7.2. Assessments of the Participants

Demographic, clinical, and cancer characteristics will be collected on paper or via RedCap.

7.2.1. Demographics (APPs, Fellows, Patient, and Caregivers)

APPs/hematology/oncology fellows age, race, ethnicity gender, and years in practice since completion of training will be collected. For hematology/oncology fellows, years in fellowship will be collected.

Patient and caregiver's age, race, ethnicity, gender, highest level of education achieved, employment status, and marital status. Caregiver's relationship to the patient will also be inquired. This will only be collected at baseline.

7.2.2. Clinical and Cancer Characteristics (Patient)

ECOG performance status, comorbidities, medications, weight, height, BMI, diagnosis and date of diagnosis, prior hematologic malignancies, stage/risk group, and treatment regimen will be abstracted from the medical records. This information will only be collected at baseline.

In addition, we will collect the following from the medical records (up to 5 years following their participation in the study or death) which will provide end of life quality indicators. We have previously collected this information in a retrospective fashion and will use similar procedures to extract this information prospectively from the medical records.

- Hospice enrollment (and timing relative to death)
- Palliative care referral (and timing relative to diagnosis)
- Chemotherapy administration within the last 2 weeks of life
- Completion of advance directives which include MOLST forms, living will, durable power of attorney for healthcare, and healthcare proxy forms (and timing related to diagnosis and death)
- Do not resuscitate order /Do not intubate order (and timing related to diagnosis and death)
- Emergency department visits in the last 30 days of life
- ICU admissions in the last 30 days of life
- Hospitalization in the last 30 days of life (number of hospitalizations, reasons for hospitalizations)
- Use of life-sustaining treatments (e.g., mechanical ventilation, vasopressors,

- tracheostomy, dialysis for acute kidney injury, percutaneous endoscopic gastrostomy) in the last 30 days of life
- Transfusion in the last 7 days of life
- Place of death (home, hospital, facility, etc.)
- Inpatient mortality rate

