3.5 Inclusion and Exclusion Criteria for Patients (Aim 2)

Inclusion criteria:

- Age \geq 60 years
- A diagnosis of hematologic malignancy [including but not limited to acute leukemia, myeloid malignancies (e.g., atypical CML, MDS/MPN overlap syndromes, CMML), multiple myeloma, lymphoma, or any other hematologic malignancies based on the primary oncologist's judgment]
- Able to provide informed consent
- Being managed in the inpatient setting
- English-speaking

Version Date: 5/10/23

PRMC#: UOCPC22039

Study Protocol

ClickIRB #: STUDY00007403

Exclusion criteria

- None

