7.0. Treatment Protocol

7.1. Study Outline

For Aim 1, we will identify all inpatient APPs. We will email the intervention materials to them before the focus group meetings. Following this, the study team will conduct in-person or zoom/phone focus group interviews with APPs for 30-60 minutes. First, we will explain the rationale of the study. Second, we elicit preferences and feedback regarding the inpatient APP-delivered ACP intervention. This will include preferences on SICG training (i.e., length of training, in-person vs. virtual, live vs. prerecorded) and on SICG implementation (i.e., organization and content of the SICG including language that should be added, removed, or changed, workflow).

For Aim 2, we will screen and consent eligible patients of treating physicians at WCI. After consent, the study subject and caregiver (if applicable) will complete demographics and baseline measures. The patient will be provided with the “Patient Preparation Letter” following completion of baseline measures and prior to the inpatient ACP visit. This will allow the patient to review the document and prepare for their discussion with the APP/hematology/oncology fellow. Following this and during the same hospital admission, an inpatient ACP visit will be scheduled with an APP/hematology/oncology fellow on the inpatient malignant hematology service. The APP/hematology/oncology fellow will use the “Serious Illness Care Guide” during this visit with the patient. The APPs who participated in Aim 1 of this study have already completed training on how to use this guide. For additional APPs who may join in Aim 2 and hematology/oncology fellows who will join in Aim 2, they will complete the same training session as the original group of APPs on how to use this guide. Finally, at the end of the visit, the patient will be provided with the “Family Guide” (either from the APP/hematology/oncology fellow or the study coordinator). The patient can use this guide to help communicate with their family about the visit that they had with the APP/hematology/oncology fellow. The APP/hematology/oncology fellow will be able to access with the Epic Serious Illness Conversation Template on Epic and will document their conversation with the patient using the template in the electronic medical record.

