Models for comparison with historical control: For AML and MDS specifically, we will compare outcomes (EOL quality indicators) to a historical control cohort, which we have previously collected and published.¹² Rates of EOL outcomes in the historical cohort are shown in Figure 4, and range from <20% (chemotherapy in the last 14 days of life) to >80% (hospitalization in the last 30 days of life). Rates of EOL outcomes in this study population will be graphically summarized in a similar fashion. We aim to compare EOL outcome measures in this study population to EOL outcomes seen in the historical cohort referenced above.

Figure 1: End of life quality indicators (2014-2019)

Version Date: 5/10/23

PRMC#: UOCPC22039

Study Protocol

ClickIRB #: STUDY00007403

Qualitative analyses: All inpatient ACP visits and interviews will be audio-recorded by study personnel and then transcribed by a professional transcription service. Inpatient ACP visit transcript themes will focus on the APPs/hematology/oncology fellows ability to assess EOL concerns brought up by the patient and caregiver, as well as advance directive completion. Post-intervention interview themes will focus on participant experience during the inpatient ACP visit and feedback which will be used to further optimize the study procedures and intervention.

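### The end-of-life utilization indicators are counted back from death with no anchor at the ACP visit, so for early deaths the entry admission and pre-visit care can be scored as post-intervention outcomes

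*Combined protocol and SAP*

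**What the plan says.** Section 3.5 makes inpatient status an entry criterion: "Being managed in the inpatient setting". Section 7.1 places the intervention in that stay: "Following this and during the same hospital admission, an inpatient ACP visit will be scheduled".

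Section 7.2.2 lists the utilization indicators to be abstracted from the record. All run backward from death:

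- 30 days: "Hospitalization in the last 30 days of life (number of hospitalizations, reasons for hospitalizations", "ICU admissions in the last 30 days of life", "Emergency department visits in the last 30 days of life", and life-sustaining treatments.
- 14 days: "Chemotherapy administration within the last 2 weeks of life".
- 7 days: "Transfusion in the last 7 days of life".

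Where 7.2.2 asks for timing (hospice, palliative care referral, advance directives, resuscitation orders), the reference points are diagnosis and death, never the ACP visit. The patient table in 9.1.2 nevertheless places the indicators in the post-intervention column. Section 2.2 treats end-of-life care as a preliminary efficacy outcome. For AML and MDS, section 8.2.2 sets the results beside earlier patients: "We aim to compare EOL outcome measures in this study population to EOL outcomes seen in the historical cohort referenced above".

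**The concern.** If a patient dies soon after the visit, part of the outcome window lies before the intervention was given. Two things follow.

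- **Hospitalization.** The patient was in hospital at the visit, so any death within 30 days of it is positive whatever the conversation achieved. The index stay can have the same effect on somewhat later deaths: someone discharged on day 10 after the visit who dies on day 35 was still in hospital within the final 30 days.
- **The other utilization indicators.** An ICU stay, emergency arrival, chemotherapy dose or transfusion that was over before the visit can be recorded as a post-intervention outcome. This is possible, not certain.

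At stake is the reading of the efficacy part of section 2.2. The forced positives raise the hospitalization rate by an amount set by early mortality, not by the intervention, and a larger sample does not remove them. No passage says that the historical cohort was selected on being in hospital, so it need not carry the same pull.

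**Working it through.** **Does any text close the gap?** No section starts a window at the visit, excludes the index admission, requires a minimum survival after the visit, or plans a landmark or sensitivity analysis. The 5-year limit in 7.1 and 7.2.2 sets how long records are collected; it does not cut the look-back. Section 7.2.3.9 collects ACP documentation both at baseline and after the intervention, but no such pairing exists for utilization. The mechanism therefore follows from the definitions and needs no outside figure.

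**Is there a planned figure to reproduce?** Not for these indicators. The only precision statement in 8.2.2 concerns the feasibility rate, which this point does not touch.

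**Size: inputs.** N = 50 (3.7). Follow-up is to death or 5 years (7.1). Median survival is 6 to 12 months, given in the background for older AML. Two assumptions are added: survival is exponential from the visit, and the AML medians serve as a scale for a mixed inpatient group. One month is 30.4375 days.

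**Step 1: share of patients whose window crosses the visit.** F(d) = 1 − 2^(−d/median).

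| Window | Median 12 months | Median 6 months |
|---|---|---|
| 30 days | 5.5% (2.8 of 50) | 10.8% (5.4 of 50) |
| 14 days | 2.6% (1.3 of 50) | 5.2% (2.6 of 50) |
| 7 days | 1.3% (0.7 of 50) | 2.6% (1.3 of 50) |

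Among deaths within 30 days, about 15 of the 30 days fall before the visit on average.

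**Step 2: as a share s of deaths within 5 years.** s = F(30 days)/F(5 years).

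- Median 12 months: 0.0553/0.9688 = 5.7%.
- Median 6 months: 0.1076/0.9990 = 10.8%.

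**Step 3: effect on the hospitalization rate.** Let p be the rate that would be seen if the index admission forced no positives. Recorded rate = s + (1 − s)p, so the lift is s(1 − p).

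- p = 60%: 62.3% to 64.3%, a lift of 2.3 to 4.3 points.
- p = 80%: 81.1% to 82.2%, a lift of 1.1 to 2.2 points.

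**Step 4: what would make it larger.**

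- *Higher early mortality.* At an assumed 3-month median, s = 20.4%, and p = 60% is recorded as 68.1%.
- *An early data cut.* Suppose accrual is uniform over the 18 months in 3.7 and data are cut at month 24, in line with the two-year project in 1.6. Follow-up is then uniform on 6 to 24 months. The share dead by the cut is 1 − (m/ln 2)/18 × (2^(−6/m) − 2^(−24/m)) for median m in months: 0.560 at m = 12 and 0.790 at m = 6. So s = 0.0553/0.560 = 9.9% and 0.1076/0.790 = 13.6%. At p = 60% the lift is 4.0 and 5.4 points.
- *A long index stay.* If it runs 14 days past the visit (assumed), deaths up to day 44 are positive through that stay alone: F(44 days) = 8.0% and 15.4% of patients at medians of 12 and 6 months.

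**The case against.** **Death-anchored windows are deliberate.** Section 1.2 presents these domains as established quality indicators, and 7.2.2 says that collection will follow the procedures used retrospectively before. A shared definition is what makes the historical comparison possible. This stands, and the all-decedent rates should not be replaced.

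**The obvious repair is worse than the fault.** Counting only events that began after the visit would score a patient who never leaves hospital and dies there on day 20 as not hospitalized, and would drop an ICU stay that began before the visit and lasted until death. Reading the effect only from patients who died more than 30 days after the visit conditions on survival. The historical cohort has no visit date, so the cut would fall on one side only. Both points stand and shape the fix.

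**The effect is small beside the noise.** If there were 25 AML/MDS decedents with 15 positive (assumed), the exact 95% interval would be 0.39 to 0.79. The aim is secondary and the reporting descriptive. This limits the severity, but imprecision does not correct a bias, and labelling pre-visit care as post-intervention is wrong at any sample size.

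**Other outcomes still credit the intervention.** A patient who goes home on hospice and dies on day 10 is credited on hospice enrollment, place of death and inpatient mortality. The examples in 2.2 include readmission, which follows discharge by definition, and do not name hospitalization in the final 30 days. This is fair, but 8.2.2 does name that indicator, with a historical rate above 80%.

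**Stronger readings that the documents do not support.**

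- *That the bias could turn a benefit into apparent harm.* Even at an assumed early-death share of 30% and p = 60%, the recorded rate is 0.30 + 0.70 × 0.60 = 72%, still below the historical figure.
- *That every indicator is contaminated automatically.* Only hospitalization is.
- *That early deaths fail a study endpoint for MOLST completion more than 30 days before death.* Section 1.3 reports that cut-off as background; 7.2.2 records timing without it.

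**Conclusion.** The point holds as a definitional gap of modest size. For deaths within 30 days of the visit, hospitalization is positive by eligibility, and the other utilization indicators can include care given before the visit.

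The size rests on exponential survival and on AML medians applied to a mixed inpatient group. Under those assumptions about 6–11% of deaths over 5 years are affected, and the recorded hospitalization rate rises by about 2–4 points at a true 60%, or 1–2 points at 80%. It would be larger with higher early mortality or an early cut; the documents give no early mortality figure and specify no early cut.

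For hospitalization the bias runs against the intervention, so it can mask a benefit. Feasibility, the primary metric, is unaffected.

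**What to change.** **In 7.2.2,** record the ACP visit date, the visit-to-death interval and the index discharge date. Flag each hospitalization, emergency visit, ICU stay, life-sustaining treatment, chemotherapy administration and transfusion as ended before the visit, ongoing at the visit, or begun after it.

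**In 8.2.2,** keep the all-decedent, death-anchored rates as the figure compared with the historical cohort. Add a sensitivity display that:

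- (a) splits decedents at 30 days or less and more than 30 days from visit to death; and
- (b) excludes only events that ended before the visit, still counting care ongoing at the visit or begun after it.

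Part (b) mainly affects the non-hospitalization indicators. The index stay is ongoing at the visit and remains counted, so part (a) and the index discharge date are what show its contribution to hospitalization.

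State that the group surviving more than 30 days is conditioned on survival, and that its rates are not to be compared with the unrestricted historical rates unless a matching rule is applied to that cohort.

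**Cost:** a few dates and one flag per event, from records already being abstracted, plus a short addition to 8.2.2. The subgroups will be small: on the figures above, about 3 to 5 of 50 patients would die within 30 days of the visit.

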7.2.3. Measures

Measures will be collected via in-person, done via email on redcap as a survey option, or from mailings sent to the participants.

7.2.3.1. Functional Status (Patient) – baseline only – Aim 2

Activities of daily living (ADL): ADLs are measures of self-care. ADL independence will be assessed using the Katz Index of Independence in Activities of Daily Living, commonly referred to as the Katz ADL. The Katz ADL is the most appropriate instrument to assess functional status as a measurement of the client's ability to perform activities of daily living independently. Clinicians typically use the tool to detect problems in performing activities of daily living and to plan care accordingly. The Index ranks adequacy of performance in the six functions of *bathing, dressing, toileting, transferring, continence, and feeding*. Clients are scored yes/no for independence in each of the six functions. A score of 6 indicates full function, 4 indicates moderate impairment, and 2 or less indicates severe functional impairment.²²

Instrumental Activities of Daily Living (IADL): Self-reported functional status will be assessed using the IADL subscale of the Multidimensional Functional Assessment Questionnaire: Older American Resources and Services (OARS). The IADL subscale consists of seven questions rated on a three-point Likert scale. It measures the degree to which an activity can be performed independently.²³

Fall History: A self-reported history of falls in the past year will be recorded. A history of a recent fall has been demonstrated to be independently predictive of increased risk for chemotherapy toxicity in older cancer patients.²⁴

7.2.3.2. Nutritional status (Patient) – baseline only – Aim 2

Self-reported weight loss in the past 6 months.

7.2.3.3. Social Support (Patient) – baseline only – Aim 2

Patients self-report their living situation and their main social support.

7.2.3.4. Psychological Health (Patient and Caregiver) – baseline only – Aim 2

Geriatric Depression Scale-15: A 15-item screening instrument for depressive symptoms in older adults.²⁵

7.2.3.5. Cognition (Patient) – baseline only – Aim 2

Mini-Cog (baseline only): Brief, cognitive screening test that is used to evaluate cognition in older adults.²⁶

7.2.3.6. Health Literacy (Patient) – baseline only – Aim 2

Cancer health literacy (CHLT-6): A brief instrument to determine whether an individual has limited cancer health literacy.²⁷

7.2.3.7. Disease Understanding (Patient) – baseline and post-intervention – Aim 2

Disease Understanding – Patient: A questionnaire assessing patient's prognostic understanding of illness. They will also be asked if prognostic information was provided.

7.2.3.8. ACP Engagement Survey (Patient) – baseline and post-intervention – Aim 2

ACP Engagement Survey: 15-item engagement survey that assess patient self-efficacy and readiness for identification of a medical decision maker, identification of personal values, and flexibility in decision making and communication with their physician.

7.2.3.9. ACP Documentation – baseline and post intervention – Aim 2

Data on ACP documentation will be collected through the electronic medical record. This will include explicit statement of the patient's medical preferences for EOL care in a note, scanned MOLST form that was completed with their clinician, and/or scanned healthcare proxy form that was completed with their clinician.

7.2.3.10. Acceptability Questionnaire (Patient and APP/Fellow) – post-intervention only – Aim 2

Patient Acceptability Questionnaire (Aim 2): A questionnaire used in the original

Version Date: 5/10/23

PRMC#: UOCPC22039

Study Protocol

ClickIRB #: STUDY00007403

evaluation of the SICP implementation to assess the impact of the serious illness conversation on the patient's understanding and perception of their diagnosis.²⁸

Clinician Confidence Questionnaire (Aim 2): A questionnaire used in the original study evaluating the SICP implementation to assess clinician's self-perceived ability to implement the SICP in real practice. This will be used in Aim 2 at 3 time points: before the SICP training (led by [name]), after the SICP training, and at completion of the study (APPs and hematology/oncology fellows will complete the same training).²⁷

Clinician Acceptability Questionnaire (Aim 2): A questionnaire used in the original study evaluating the SICP implementation to assess the clinicians experience in using the SICP with patients.²⁷

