2.2. Secondary Aim

To assess the feasibility of an inpatient ACP intervention, as well as the preliminary efficacy of the intervention on completion of advance directives (e.g., MOLST form, healthcare proxy form) and on EOL care (e.g., intensive care unit admissions, life-sustaining treatments, readmission rates, hospice enrollment, inpatient death).

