4.3 Duration

Aim 1: The qualitative section of this study involves focus group interviews with APPs for 30-60 minutes. Participating APPs will be interviewed by the study team either in-person (in a private space) or via zoom. Interviews will be audio-recorded, uploaded to Box, and subsequently deleted from the audio-recorder.

Aim 2: At study initiation, APPs/hematology/oncology fellows will undergo a skill-based training session of the SICG (3 hours). APPs and hematology/oncology fellows will undergo the same skill-based training session. The SICG training session is a 2.5 to 3-hour training session that will be conducted via zoom or in-person and led by [name] (palliative care physician). This training session will include standardized patient encounters for APPs/hematology/oncology fellows to practice using the SICG under the direct supervision of [name] with real time feedback.

At baseline, study patients and consented caregivers will complete demographics and baseline measures. We will also collect demographic information from APPs/hematology/oncology fellows. We will perform a geriatric assessment that assesses the patient's overall health status

Version Date: 5/10/23

PRMC#: UOCPC22039

Study Protocol

ClickIRB #: STUDY00007403

prior to ACP intervention. Following this, we will schedule an ACP visit with an APP/hematology/oncology fellow on the inpatient malignant hematology service during the same hospital admission. Their caregivers can join via in person, zoom, or phone (depending on COVID restrictions). During the ACP visit, the APP/hematology/oncology fellow will discuss ACP and EOL care and may facilitate completion of advance directives and a MOLST form if appropriate. This visit will be recorded. After the visit, they will complete post-intervention measures. Within 4 weeks of the ACP visit, we will conduct a semi-structured interview with the patient and caregiver (if available) either via video, phone, or in-person to elicit their experience with the visit and feedback on the ACP intervention. We will also conduct a semi-structured interview with APPs/hematology/oncology fellows who enrolled patients at the end of the study.

All audio-recordings will be uploaded to Box, transcribed by a professional transcription service, and subsequently deleted from the audio-recorder. After the study is completed, all participant data will be maintained for 7 years at URMC and will be kept in a password-protected database.

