Coaching on use of the SICG	Palliative care faculty offered coaching to intervention clinicians on use of the SICG by phone, email, or in person.

Version Date: 5/10/23

PRMC#: UOCPC22039

Study Protocol

ClickIRB #: STUDY00007403

Table 2 Adapted SICG for patients with hematologic malignancies.

Serious Illness Conversation Guide	
CONVERSATION FLOW	
1. Set up the conversation	

• Introduce purpose• Prepare for future decisions• Ask permission	
2. Assess understanding and preferences	
3. Share understanding	

• Share prognosis if appropriate• Frame as a “wish”, “hope” statement• Allow silence, explore emotion	
4. Explore key topics	

• Values/Goals• Worries or Fears• Strength• Tradeoffs• Caregiver and family	
5. Close the conversation	

• Summarize• Make a recommendation• Welcome suggestions• Check in with patient• Ask for involvement of caregiver and family• Affirm commitment	
6. Document your conversation	

• Consider creating a note that is separate from the daily progress note OR• Consider documenting conversation at the beginning or end of a daily progress note	
7. Communicate with key clinicians	

Completion Document ID: 5306250

This material has been modified by us (Wilmot Geriatric Hematology Research Group). The original content can be found at www.ariadnelabs.org and is licensed by Ariadne Labs: A Joint Center for Health Systems Innovation (www.ariadnelabs.org) at Brigham and Women's Hospital and the Harvard T.H. Chan School of Public Health. Licensed under the Creative Commons Attribution-NonCommercial-ShareAlike 4.0 International License, <http://creativecommons.org/licenses/by-nc-sa/4.0/>

Version Date: 5/10/23

PRMC#: UOCPC22039

Study Protocol

ClickIRB #: STUDY00007403

Serious Illness Conversation Guide

SET UP	
• "Many patients like to talk about what is ahead with their illness and think about what is important to them. This is part of the care we provide for all of our patients to make sure that we provide the care you want – is this something you would like to talk about?"

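### Does the ACP documentation measure in section 7.2.3.9 need a written rule that sets the study-visit note apart?

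*Combined protocol and SAP*

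**What the plan says.** Section 7.2.3.9 lists three sources to be read from the electronic record at baseline and post-intervention. The first two are "medical preferences for EOL care in a note, scanned MOLST form that was completed with their clinician"; the third is a scanned healthcare proxy form, joined by and/or. It gives no scoring rule, no combined endpoint and no denominator.

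The intervention creates a chart entry. Under section 7.1 the APP or fellow "will document their conversation with the patient using the template in the electronic medical record". Step 6 of the adapted guide (section 6.0, Table 2) is softer: "Consider creating a note that is separate from the daily progress note", or else place the text within the daily note. The conversation starts only with the patient's agreement, since the guide first asks "is this something you would like to talk about".

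On timing, section 4.3 says only this of patients and caregivers: "After the visit, they will complete post-intervention measures". The same section says the clinician "may facilitate completion of advance directives and a MOLST form if appropriate".

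The outcome carrying the preliminary-efficacy aim is stated elsewhere. Section 2.2 names "completion of advance directives (e.g., MOLST form, healthcare proxy form"). Section 7.2.2 spells out what is collected, with timing relative to diagnosis and death: "Completion of advance directives which include MOLST forms, living will, durable power of attorney for healthcare, and healthcare proxy forms". Notes appear in neither place. Section 8.2.2 plans descriptive summaries of all measures, with exact binomial intervals for the feasibility rates.

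**The concern.** There is no concurrent control, so a before/after change is the only contrast available for this measure. If charting the visit is part of the intervention and a charted preference is also part of the measure, delivering the visit moves the measure by itself. A note rate, or a rate counting any of the three sources, could go up without one additional MOLST or proxy form. Placed beside advance-directive completion, such a rise might be taken as support for the hypothesis in section 2.3, when part of it shows only that the visit was held and written up. The plan also leaves open whether the three sources are reported together, who is in the denominator, and when the post-intervention search of the record ends.

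**Working it through.** The plan states no rate, target or test for ACP documentation, so there is no figure to reproduce. The check has two parts.

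**1. Which planned results use the note?**

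| Result | Where defined | Uses the note? |
|---|---|---|
| Advance-directive completion | 2.2, 7.2.2 | No: MOLST, living will, durable power of attorney, proxy form |
| Retention (feasibility) | 7.2.3.11, 8.2.2 | No: completion of the visit or of study components |
| Recruitment | 7.2.3.11, 8.2.2 | No |
| Historical comparison in AML/MDS | 8.2.2, indicators listed in 7.2.2 | No |
| ACP documentation, note item | 7.2.3.9 | Yes, descriptive only |
| Any-of-three rate | Not defined anywhere | Would, if someone constructed it |

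Only the note item is affected. The forms in 7.2.3.9 are named individually, and 7.2.2 collects forms again with their timing. They can therefore be separated from notes without new data.

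**2. How far could the note item move through delivery alone?**

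Let b be the share of patients with a qualifying note at baseline, v the share of enrolled patients who complete the visit, and q the share of visit notes that contain an explicit preference statement. If no other notes are added, and v and q do not depend on baseline status:

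rise = (1 − b) × v × q

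None of the three inputs is in the protocol. The value v = 0.70 is taken from the benchmark in 8.2.2 purely as an illustration; there it is a share of patients approached, not of those enrolled. With q from 0.25 to 1:

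- b = 0.20: 0.80 × 0.70 × q = 0.14 to 0.56, or 7 to 28 of 50 patients.
- b = 0.40: 0.60 × 0.70 × q = 0.105 to 0.42, or about 5 to 21 of 50. At q = 1 the rate goes from 20/50 to 41/50.
- b = 0.80: 0.20 × 0.70 × q = 0.035 to 0.14, or about 2 to 7 of 50.

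The same formula serves an any-of-three rate with no new forms, if b is the baseline any-of-three rate. The plan contains no such rate.

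The span from 3.5 to 56 points shows that the assumptions drive the answer. It illustrates the mechanism and is not an estimate for this trial. Two features of the text hold q below 1: a note qualifies only if it states end-of-life care preferences explicitly, and the patient may decline the conversation.

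Reporting the items one by one costs no precision. Each keeps n = 50, and the exact 95% interval at 25/50 runs from 0.355 to 0.645, a width of 0.29.

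**The case for a change.** The best case for amending the plan is that the remedy is cheap and should come before abstraction. Because step 6 allows the visit to be written up inside a daily progress note, a visit-related statement may be hard to recognise later. The patient table in 9.1.2 has no ACP-documentation row, and neither the denominator nor the extraction window is stated. A few sentences and one row would settle all of this.

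Some of that stands. An analyst should list the three sources separately, mark preference statements that come from the study visit, and state the denominator and window used. This is ordinary practice in a descriptive pilot report and can be done within the text as it is. The visit is scheduled by the study, audio-recorded and conducted by a consented clinician, so its date and author are known even when the text sits in a progress note. The absent table row is clerical: advance directives are among the end-of-life indicators of 7.2.2, which do have a row in 9.1.2.

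The rest is less persuasive. Basing efficacy on forms and not on notes is what 2.2 and 7.2.2 already do. Treating the visit's note as mere delivery is also debatable. Section 1.6 makes better access to ACP a goal, so a newly charted preference is an intended result, and forms may come out of the same visit without being discounted. A stricter rule, such as counting only forms dated on or after the visit, would bring problems of its own. It is undefined for consented patients who have no visit, it omits forms signed between the preparation letter and the visit, and it has no end date while records are followed for up to 5 years.

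**Conclusion.** The plan does not set the study-visit note apart, and the note item would rise partly through delivery. No change is needed, because no efficacy or feasibility conclusion rests on that item: its effect on advance-directive completion, retention, recruitment and the historical comparison is nil. On the note item itself the size is unknown; the illustrative figures depend wholly on assumed values of b, v and q. The conclusion assumes that the report keeps the sources apart, as 7.2.3.9 names them, and does not present a combined rate as evidence of efficacy. If a combined rate were later put forward in that role, the point would need to be reopened.
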